## 5.4 Safety Endpoint 3: Long-term Device Related SAEs

Objective: To quantify real-world long-term safety using the MANTA device.

Endpoint: The percentage of patients with one or more events on ipsilateral leg with MANTA device as described in the main safety endpoints beyond 30 days for each event:

- VARC-2 major complication
- VARC-2 minor complication (with no major VARC-2 complication)

Subjects to include: All subjects that have enrolled in the longer-term follow-up with a procedure attempt will be included in this analysis.

Statistical analysis (patient based): The number of subjects, percentage of patients and 95% confidence intervals for the percentage of subjects will be calculated at a minimum for subjects experiencing a major VARC2 complication and again for minor VARC2 complication.

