The 3 Major Complications reported were the only safety events that were classified as potentially or definitely device-related SAEs. For 2 of these events the Sponsor concluded that these events were a result of minor manufacturing deficiencies. Necessary corrective action has been taken to improve the manufacturing process and limit the associated safety risk.

In total, 10 AEs described an access site related hematoma > 6 cm. The investigator who treated these subjects, confirmed that this concerned an ecchymosis in 5 cases (50%), which is sometimes difficult to distinguish from a hematoma. This information was accompanied by ultrasound data in 3 cases, where the hematoma at the artery was assessed as 0.96, 2.28 and 0.82 cm². The 5 remaining cases concerned true hematomas based on visual assessment and available ultrasound data and those were classified as Minor Complications. No other Minor Complications were reported during the course of the study.

The AE termed 'stenosis at the access site' has only been reported at site 01. The observed difference in frequency proportion may be due to an interest bias. The involvement of an independent interpreter, e.g. by use of a qualified core lab, would limit the interpretation bias in future studies.

A large number of unrelated AEs can be anticipated with a study population as included in this study, with a mean age of 79.5 years (Standard deviation: 8.3 years; Median 80.7 years; Minimum 42.6 years; Maximum 90.4 years) and who are undergoing a significant intervention. Additionally, physical exam at baseline revealed that 46 subjects (92%) were suffering from one or more comorbid conditions prior to MANTA treatment.

Performance

Hemostasis Success was obtained in 94% of the subjects. The mean Time to Hemostasis reported in this study was 2 minutes and 23 seconds. The minimum reported Time to Hemostasis was 2 seconds and 74% of the subjects had a time to hemostasis reported that was less than 1 minute. These results indicate excellent performance of the device, given that the MANTA device is used for vascular closure of very large punctures. Outer diameters of the index procedure sheaths which the 18F MANTA device closed were as large as 24.5F (8.17 mm).

The subjects for whom no Hemostasis Success was obtained (n=3, 6%) were the same subjects for whom a Major Complication was reported, as well as for whom a Time to Hemostasis of more than 10 minutes was reported.

Conclusion

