Interim analysis may be performed throughout the duration of the registry.

8.5. *Minimum and Maximum Patient Recruitment for Analysis*

Study enrollment will be competitive. There is no minimum or maximum number of patients that can be enrolled per site.

8.6 *12M Follow-Up Analysis and Minimization of Bias*

A minimum of 100 and up to a maximum of 120 subjects will be re-enrolled into the registry to complete the 12M follow-up visit. Bias will be minimized by contacting subjects who were treated within a specific timeframe designated by the Sponsor (for example, September 2018 to July 2019). Sites will be extended an invitation to participate in the study if they have enrolled at least 10 subjects within the identified timeframe in order to justify study costs incurred to keep the site open, submit amendments to the appropriate ethics committee, bandwidth of the site research team, etc.

The subset followed to one year is expected to be similar to the overall cohort in baseline patient characteristics. Baseline data for the 12M subset will be analyzed and compared to the overall cohort to demonstrate that the subset is representative of the overall cohort. If there are differences in the baseline characteristics of the subset and the overall cohort, these will be further evaluated and assessed as to their potential impact on the 12M results.

To test for generalizability of 12-month outcomes, patients undergoing 12-month follow-up will be compared to patients not undergoing 12-month follow-up in a pre-specified analysis of baseline demographics, clinical characteristics, procedural variables and in-hospital/30-day end-point outcomes.

Only AEs related to the MANTA access site or the ipsilateral leg will be collected at the 12M visit. AE data from the 12M visit will be analyzed separately from the primary safety endpoint, as 12M data will only be available on a subset of the study cohort and the primary safety endpoint is events through 30-days.

9. Adverse Events

9.1. *Definitions*

Refer to Section 4 for the definitions of the following terms associated with adverse events:

- Adverse Event
- Adverse Device Effect
- Device Deficiency
- Serious Adverse Event
- Serious Adverse Device Effect
- Unanticipated Serious Adverse Device Effect

9.2. *Potential Adverse Events and Adverse Device Effects*

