## 5.2 Safety Endpoint 1: VARC-2 Major Complications

Objective: To quantify the real-world VARC-2 major femoral vascular complication incidence using the MANTA device.

Endpoint: The percentage of patients with one or more VARC-2 Major femoral vascular complications as adapted from VARC-2 definitions within 30 days following procedure. The classification of "major" will be determined by the CEC and will be recorded in the CEC spreadsheet.

VARC-2 Major femoral vascular complication definition:

- Femoral access site or access-related vascular injury (dissection, stenosis, perforation, rupture, arterio-venous fistula, pseudoaneurysm, hematoma, irreversible nerve injury, compartment syndrome, percutaneous closure device failure) leading to death, life-threatening or major bleeding; OR,
- downstream distal embolization (lower extremities) requiring surgery or resulting in amputation; OR,
- the use of unplanned endovascular or surgical intervention associated with death, major femoral bleeding; OR,
- any new ipsilateral lower extremity ischemia documented by patient symptoms, physical exam, and/or decreased or absent blood flow on lower extremity angiogram; OR,
- surgery for femoral access site-related nerve injury; OR,
- permanent femoral access site-related nerve injury.

Subjects to include: All subjects with a procedure attempt will be included in this analysis.

Statistical analysis (patient based): The number of subjects, percentage of patients and 95% confidence intervals for the percentage of subjects will be calculated at a minimum for subjects experiencing any type of major complication as previously defined. Additional summaries may include splitting into adverse event type as collected via the case report forms.

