## 5.3 Safety Endpoint 2: VARC-2 Minor Complication

Objective: To quantify the real-world VARC-2 minor femoral vascular complication incidence using the MANTA device.

Endpoint: The percentage of patients with one or more VARC-2 Minor femoral vascular complications (and no major VARC-2 complications) as adapted from VARC-2 definitions within 30 days following procedure.

Minor femoral vascular complication definition:

- Access site or access-related vascular injury (dissection, stenosis, perforation, rupture, arterio-venous fistula, pseudoaneuysms, hematomas, percutaneous closure device failure) not leading to death, life-threatening or major bleeding; OR,
- downstream distal embolization (lower extremities) treated with embolectomy and/or thrombectomy and not resulting in amputation; OR,
- any unplanned endovascular stenting or unplanned surgical intervention not meeting the criteria for a major vascular complication; OR,

- vascular repair or the need for vascular repair (via surgery, ultrasound guided compression, transcatheter embolization, or stent-graft); OR,
- percutaneous closure device failure\*.

\*Failure of a closure device to achieve hemostasis at the arteriotomy site leading to alternative treatment (other than manual compression or adjunctive endovascular ballooning).

Subjects to include: All subjects with a procedure attempt will be included in this analysis.

Statistical analysis (patient based): The number of subjects, percentage of patients and 95% confidence intervals for the percentage of subjects will be calculated at a minimum for subjects experiencing any type of minor complication as previously defined. Additional summaries may include splitting into adverse event type as collected via the case report forms.

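### SAP 5.4 is labelled as device-related serious events but counts VARC-2 events by leg and time alone, so limb events unrelated to MANTA may enter the 12-month rate

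*SAP*

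**What the plan says.** SAP 5.4 is headed "Safety Endpoint 3: Long-term Device Related SAEs", and its objective is to quantify long-term safety in real-world use of the device. The endpoint is the percentage of patients with "one or more events on ipsilateral leg with MANTA device as described in the main safety endpoints beyond 30 days", reported separately for VARC-2 major complications and for minor complications without a major one. It covers subjects who entered the extended follow-up and gives a 95% confidence interval for each rate.

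The event definitions are those of the 30-day endpoints. The major list in SAP 5.2 includes "any new ipsilateral lower extremity ischemia documented by patient symptoms, physical exam, and/or decreased or absent blood flow on lower extremity angiogram". The minor list in SAP 5.3 includes "any unplanned endovascular stenting or unplanned surgical intervention not meeting the criteria for a major vascular complication; OR", followed by a separate item for vascular repair or the need for it.

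Protocol 8.6 sets what is collected: "Only AEs related to the MANTA access site or the ipsilateral leg will be collected at the 12M visit". Protocol 9.7 states that events found in the 12-month subset are not adjudicated, because the safety endpoints end at 30 days.

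**The concern.** The title promises device-related serious events, while the definition selects events by location and date. In the first 30 days after a large-bore puncture, a vascular event in that leg is plausibly due to the access. Over the following 11 months that presumption weakens, and the plan puts nothing in its place.

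This endpoint is the SAP's formal statement on long-term safety. If its rate mixes late device effects with limb events of other cause, a reader who trusts the title will take the whole rate as attributable to MANTA. In a subset of 100 to 120 patients, a few events determine the result.

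**Working it through.** The plan states no expected rate, power or sample-size basis for this endpoint, so there is no figure to reproduce. The check is a comparison of the texts, followed by arithmetic for scale.

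**1. Can the title act as the filter?** If it governed, non-serious events would drop out. But SAP 5.4 lists minor complications as a reported category with no seriousness condition. Title and definition conflict, and a programmer would follow the definition.

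**2. Which components lack a link to the access or the device?**

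| Component | Class | Qualifier |
|---|---|---|
| Vascular injury | Major and minor | Must be at the access site or access-related; does not name the index access |
| Nerve injury or nerve surgery | Major | Must be related to the femoral access site |
| Unplanned intervention | Major | Needs death or major femoral bleeding: "the use of unplanned endovascular or surgical intervention associated with death, major femoral bleeding" |
| New ipsilateral ischemia | Major | None |
| Unplanned stenting or surgery | Minor | Unplanned only |
| Vascular repair | Minor | None |

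The last three rows can be met by an event unrelated to MANTA.

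**3. What screens relatedness, and when?** Up to 30 days, SAP section 3 and Protocol 9.7 send the CEC those events that the investigator rates possible, probable or definite, and the safety endpoints use CEC-adjudicated data. Other outcomes may be adjudicated as an option. At 12 months there is no CEC step. Neither document says who then assigns VARC-2 class.

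**4. Are relatedness data available?** Yes. Under Protocol 9.3 the investigator rates every reported AE against the device. SAP 5.6 falls back on the investigator rating in its AE and SAE tables where no CEC rating exists. SAP 5.4 does not invoke that rating, and the day 31 to 12-month summary in SAP 5.6 is split by seriousness only.

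**5. Scale.** N = 100 to 120 (SAP section 2).

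- Effect of one unrelated patient: 1/100 = 1.00 point; 1/120 = 0.83 point.
- Exact (Clopper-Pearson) 95% intervals, assumed here because the SAP names no method. For 0 events: 0 to 3.62% (N = 100) and 0 to 3.03% (N = 120). For 3 events: 0.62 to 8.52% and 0.52 to 7.13%.
- Illustration with assumed background rates r per year, none of them from the documents, over 365 − 30 = 335 days. Let p = r × 335/365. Expected events = N × p; chance of at least one = 1 − (1 − p)^N.

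| Assumed r | Expected, N = 100 | Expected, N = 120 | Chance of ≥ 1, N = 100 | Chance of ≥ 1, N = 120 |
|---|---|---|---|---|
| 1% | 0.92 | 1.10 | 0.602 | 0.669 |
| 2% | 1.84 | 2.20 | 0.843 | 0.892 |
| 3% | 2.75 | 3.30 | 0.939 | 0.965 |
| 5% | 4.59 | 5.51 | 0.991 | 0.996 |

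These rates cover major and minor events together.

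**The case against.** The strongest reply is that counting every event in the treated leg is a cautious choice for a descriptive registry, that the objective speaks of safety in use and not of causation, and that SAP 5.6 already lets a reader separate related from unrelated events. Much of this stands. Any-cause counting is defensible and should stay, and SAP 5.6 does list MANTA-related events with onset, treatment, seriousness and relatedness. But the listing of events not related to MANTA is a reduced one, without treatment or VARC-2 class, so a reader could not reliably see which of them entered the 5.4 rate. And no listing changes what the endpoint's title claims.

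A reader might also infer more than the documents support:

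- **That any intervention in the leg counts.** It does not. The major item requires death or major femoral bleeding, and an elective stent does not meet the unplanned stenting item.
- **That a new groin puncture counts.** A puncture is not an event. Only a resulting injury or repair could qualify, because the access-related wording does not name the index access.
- **That the cohort is known to have progressive arterial disease.** SAP 5.5 records a history of peripheral artery disease but gives no prevalence. The EU pre-market report that "physical exam at baseline revealed that 46 subjects (92%) were suffering from one or more comorbid conditions prior to MANTA treatment" concerns any comorbidity in another study. Protocol 6.5.3 excludes severe peripheral artery disease, which lowers the risk without removing it.
- **That background events alone would match the 4.2% major rate in SAP Tables 2 and 3.** The assumed rates above combine major and minor events, so that comparison is not valid.

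Events in the other leg are not collected at 12 months, so they supply no background rate. That groin may itself have been used for access, so it would not be a clean control in any case.

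**Conclusion.** The mismatch is real: the title says device-related and serious, and the definition requires neither. The CEC screen that operates at 30 days is absent at 12 months, and three components can be met without any link to the access or the device. Unrelated events may therefore be counted under a device-related label, at 0.8 to 1.0 points per patient.

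This is a risk under the endpoint as written, not a demonstrated result. How 12-month events will be classified is unspecified, and the person doing it might apply a relatedness judgement informally. The total size depends on a background rate that the documents do not give; the 1% to 5% range only shows that a few events would matter. The point deserves correction because the related rate can be produced from ratings already planned.

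**What to change.** In SAP 5.4:

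1. Retitle the endpoint to match what is counted, for example: ipsilateral-leg vascular events, day 31 to 12 months. Settle the start day at the same time, since SAP 5.4 says beyond 30 days, SAP 5.5 says day 38 and SAP 5.6 says day 31.
2. Report the any-cause rate and, beside it, the rate limited to events whose relation to MANTA the investigator rated possible, probable, definite or unknown, each with a 95% confidence interval. Counting unknown as related matches SAP 5.6; leaving it out would lower the 12-month related rate against the plan's own rule.
3. State who assigns VARC-2 major or minor class to the unadjudicated 12-month events.
4. In the existing listings, flag any event attributed to a later ipsilateral puncture, where this is recorded. Do not exclude such events automatically, since that could remove a genuine late effect at the closure site.

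The cost is SAP wording, one table row for each of the major and minor rates, and a listing flag. Investigator relatedness is already planned for every reported AE. The downside is that the related rate rests on unadjudicated investigator attribution, which is why the any-cause rate stays beside it.

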## 5.5 Additional Summaries

Additional summaries will be prepared similar to the effectiveness and safety endpoints using descriptive statistics. These summaries will be prepared for the overall population, by cohort (TAVR vs not TAVR), and by MANTA device size (14 or 18 Fr) at a minimum. Some summaries will be repeated for the 12M subset as appropriate.

At a minimum the following items will be included:

1. Baseline demographics and characteristics
  - Age
  - Gender
  - BMI
  - STS score (TAVR group only)
  - Medical history (prior history of PCI, CABG, Hypertension, LVEF < 20%, kidney dysfunction (GFR < 60 umol/L), pacemaker, peripheral artery disease, stroke/CVA)
  - Medications at baseline

- i. ASCAL
- ii. Oral anticoagulants
- iii. New oral anticoagulants
- iv. Clopidogrel
- v. Heparin
- vi. Other anticoagulants

2. Procedure characteristics

- Target artery characteristics
  - i. Diameter
  - ii. Calcification
  - iii. Side (left/right/both)
  - iv. Presence of scar tissue in groin on treated side
- Procedure type
- Hemostasis time (descriptive statistics and success (<10 min) – primary performance endpoints
- MANTA procedure time
- MANTA device sizes
  - i. Instances of size mismatch (where the device size exceeds the artery size)
  - ii. Sheath-to-femoral-artery ratio
- Device deficiencies
- Procedure success (proportion of subjects with no VARC-2 major complications within 30 days)

3. 30 Day Follow-up / Exit

- Average follow-up (exit date – procedure date) in days
- Medication at each time point (during procedure, post procedure, 30 day follow-up/exit)
- Summarize type of follow-up (in person/at office or via phone call)
- Reason for study exit (as reported via eCRFs).

4. 12 Month Follow-up (for subset of 100-120 subjects)

- Average follow-up (exit day of 12 month – procedure date) in days
- Provide baseline demographics for subjects that had 12M follow-up comparing to overall population.
- Target Femoral Access Site Visual Assessment
- Adverse Events occurring on MANTA side only from day 38 to 12M visit
- Medication at each time point (12month follow-up/exit)
- Reason for study exit (as reported via eCRFs)

5. Analysis of primary and secondary safety endpoints and hemostasis by on and off-label device use. On label means meeting indications per IFU.

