7.7. Subject Follow-up

All patients will undergo an in-office follow-up examination at 30 ± 7 days post procedure to assess for any major or minor femoral vascular complications based on VARC-2 definitions or other device-related adverse events. After the 30-day follow-up is completed, subjects will be exited from the study and return to receiving medical care per their physician's recommendations.

One hundred (100) to 120 subjects will undergo an in-office examination at $12M \pm 30$ days post procedure to assess for any major or minor femoral vascular complications based on VARC-2 definitions or other device-related adverse events. Subjects who were previously exited from the study will be contacted to assess interest in participating in the 12M visit. All subjects interested in the 12M visit must voluntarily sign the informed consent form addendum for the 12M visit. Subjects completing the 12M

Essential Medical, Inc. Protocol

No. PSD-212 Rev.C

follow-up visit will be exited from the study and return to receiving medical care per their physician's recommendations.

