9.5. Reporting of Adverse Events

9.5.1 SAE and AE Reporting to Sponsor

Safety Surveillance within this registry and the safety reporting performed by both the investigator and Sponsor starts from the point of attempted MANTA placement and onward. The safety surveillance and the safety reporting will continue until the last visit has been performed, the subject is deceased. The subject/investigator concludes their participation in the study or the subject/investigator withdraws the subject from the study. All device-related SAEs from the point of attempted MANTA placement and onward will be reported to the Sponsor within 24 hours of the Investigator’s first knowledge of the event. Suspected SAEs also should be reported. Investigators should also report AEs or SAEs that are known to be unrelated to the device on eCRF.

The Investigator will forward information about a device-related SAE promptly and complete the AE and SAE report forms provided by the Sponsor, even if the information is incomplete or it is obvious that more data will be needed to form any conclusions. Additional information regarding the SAE will be recorded on the follow-up SAE form and forwarded to the Sponsor.

All MANTA device-related AEs, and AE’s associated with non-MANTA access sites, and additional outcomes not associated with MANTA device should be reported on the eCRF as soon as practicably possible. Such AEs will be recorded by their final medical diagnosis and not by each separate symptom. All AEs categorized by the Investigator as associated with MANTA leg and categorized by the Investigator as possibly, probably or definitely device-related, will be reviewed by the Clinical Events Committee for a final adjudication. The information for the event will include the date of onset and resolution, the action taken, the intervention/treatment and how the subject recovered with or without sequelae. In case of death, the relationship of death to the MANTA device and/or the study procedure will be well documented. The date on

which subject expired, what attempts were made to treat the event that led to death, the performance and functioning of the device during the event will be noted.

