  2. Long-term MANTA AEs (Day 31-12M) will be summarized by seriousness for subjects that participated in the extended follow-up for the whole cohort, the 30 day cohort and the 12M cohort.
  3. Death summaries: any subjects that died will summarized by cause of death as adjudicated by CEC. Additionally, all AEs for those subjects will be listed.

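### The SAP 5.4 long-term rate is conditional on survival and re-consent after the 30-day exit, and the planned representativeness checks, which end at day 30, dilute that selection

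*SAP*

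**What the plan says.** Protocol 7.7 ends participation at the 30-day visit: "After the 30-day follow-up is completed, subjects will be exited from the study". Exited subjects are then contacted about a 12M visit, and "All subjects interested in the 12M visit must voluntarily sign the informed consent form addendum for the 12M visit". Protocol 9.5.1 closes reporting at the same point: "The safety surveillance and the safety reporting will continue until the last visit has been performed", or until death or the end of participation.

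The objective of SAP 5.4 is "To quantify real-world long-term safety using the MANTA device". Its population is narrower: "All subjects that have enrolled in the longer-term follow-up with a procedure attempt will be included in this analysis". It counts VARC-2 major and minor complications beyond 30 days. The major definition in SAP 5.2 includes access-related injury "leading to death, life-threatening or major bleeding".

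Protocol 8.6 plans two checks on the subset. One sets its baseline data against the overall cohort, and any differences are to be assessed for their effect on the 12M results. The other compares patients with and without 12M follow-up on baseline, clinical and procedural variables and on outcomes in hospital and at 30 days. SAP 5.5 item 4 lists the first in short form: "Provide baseline demographics for subjects that had 12M follow-up comparing to overall population". Under protocol 1.9 and 8.6, invitations go to at most seven sites, each with at least 10 subjects in a treatment window set by the sponsor. The window is offered as the step that limits bias.

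**The concern.** Entry to the 12M set needs a signature given after exit. A subject who dies, moves away or refuses between exit and re-contact is in neither the numerator nor the denominator of SAP 5.4. The rate therefore describes people who were alive, reachable and willing at that time, while the objective speaks of long-term safety without restriction.

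The checks meant to support generalizability have two limits here. They use nothing after day 30, so they carry no information on deaths or refusals after exit. Their comparators, the overall cohort and all non-12M patients, also combine two different groups: eligible subjects who did not come back, and subjects never invited because of their site or treatment date. A contrast in the first group is diluted by the second and cannot be told apart from site and window selection. The treatment window does not act on survival or consent.

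At stake is how the 12M result is read. The checks could come out reassuring, and the report could then call the subset representative without anyone knowing how many eligible subjects died or declined.

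**Working it through.** The plan states no expected 12M rate and no statistical basis for its sample size, so there is no figure of its own to reproduce. Both checks are taken as carried out. N = 500 is the protocol's ceiling, 110 is the middle of the planned 100 to 120, and so 500 − 110 = 390 subjects are non-12M.

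**1. Time over which subjects are selected on survival.** The 12M visit entered with Rev B, dated 13 Aug 2019; the current Rev C is dated 26 Sep 2019. Protocol 8.6 gives September 2018 to July 2019 as an example window (334 dates). Gap = revision date − (treatment date + 30 days), floored at 0, with treatment dates assumed evenly spread:
- To Rev B: maximum 316 days, mean (316 × 317 / 2) / 334 = 150 days. The gap is above zero for 316/334 = 94.6% of dates and above 180 days for 136/334 = 40.7%.
- To Rev C: maximum 360 days, mean 193.5 days.

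This is time a subject must survive before being able to re-consent. It is not time without event data for those who return, because their later MANTA-side events are to be summarized.

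**2. Possible deaths before contact.** The only figure in the documents is the EU pre-market study (protocol 1.4): 4 of 50 died with 60 days of follow-up, 8.0% (exact 95% CI 2.2 to 19.2%). None was judged related to device or procedure. Some may have died before day 30, when they could not have been re-enrolled anyway. As an assumption, let a share d = 5 to 15% of otherwise re-enrollable subjects die before contact. The number missing per 110 re-enrolled is 110 × d / (1 − d) = 5.8 (5%), 12.2 (10%) or 19.4 (15%).

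Suppose one event is seen in 110 subjects, or 0.91%.
- If none of the missing had a late event, the rate with them included falls to 1/115.8 = 0.86% through 1/129.4 = 0.77%.
- If one of them did, it rises to 2/115.8 = 1.73% or 2/129.4 = 1.55%.

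The direction is therefore open. The exact 95% interval for 1/110 is 0.02 to 4.96%; it covers sampling error only, not selection.

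**3. What the planned checks would show.** Assume 130 to 200 eligible subjects, so m = 20 to 90 eligible but not re-enrolled. Suppose their 30-day major rate is 10 points above everyone else's.

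| m | 12M vs non-12M: 10 × m/390 | Subset vs overall: 10 × m/500 |
|---|---|---|
| 20 | 0.51 points | 0.40 points |
| 40 | 1.03 points | 0.80 points |
| 90 | 2.31 points | 1.80 points |

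At a rate of 4.2% (the weighted major rate in SAP Table 3), the 95% half-width of the 12M versus non-12M difference is 1.96 × √[0.042 × 0.958 × (1/110 + 1/390)] = 4.2 points. A 10-point contrast would be lost in it.

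**4. The same comparison within the eligible set.** With 4.2% of 110 against 14.2% of m, the full 10 points is estimated. The approximate (Wald) half-width is 15.8, 11.4 or 8.1 points for m = 20, 40 or 90. The contrast is no longer diluted, but it is imprecise.

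**The case against.** The best reply is that the plan is open about most of this. SAP 5.4 names its population. Protocol 8.6 keeps 12M adverse events apart from the primary safety endpoint because they come from a subset, and requires baseline differences to be assessed for impact. The study is descriptive. SAP 5.5 lists minimum content, and the table templates, which are not public, may include subject disposition. All of this stands. It reduces the point to a mismatch between objective and population and a weak comparator.

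The proposed comparison within the eligible set also stops at day 30. That is true: it removes the mixing with never-invited subjects, and only the flow count speaks to deaths and refusals.

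A reader might infer more than the documents support:
- **That the checks cannot detect the selection at all.** They include variables such as age, STS score and kidney function, and selection that tracks these or 30-day outcomes could appear.
- **That the 12M rate is too low.** Nothing in the documents fixes the direction, and step 2 shows it can go either way.
- **That the adverse-event summary in SAP 5.6 item 2 is clearly confined to participants.** It begins "Long-term MANTA AEs (Day 31-12M) will be summarized by seriousness for subjects that participated in the extended follow-up", but the sentence goes on to name the whole, 30-day and 12M cohorts, so its scope is ambiguous. Item 3 covers any death, though it describes no search for vital status in exited subjects.
- **That the rate should be bounded by counting deaths of unknown leg status as events.** Under the step 2 assumptions the upper bound is (1 + 5.8)/115.8 = 5.9% to (1 + 19.4)/129.4 = 15.8%. The assumed deaths drive it almost entirely, and it departs from the no-imputation rule in SAP 6.

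**Conclusion.** The concern holds in a limited form. The target of SAP 5.4 is understated, and the representativeness comparison uses a comparator that can hide the selection of interest. What the text establishes is the conditioning on survival and re-consent, the day-30 limit of the checks and the mixed comparator. The amount of dilution is illustrative: it depends on the assumed 130 to 200 eligible subjects and the assumed 10-point contrast. How many subjects died or refused before contact, and whether any had a late MANTA-leg event, cannot be derived; the effect on the rate may be nil. Survival is required up to re-consent, not to 12 months: a subject who dies after re-enrolling stays in the analysis. The primary and secondary 30-day endpoints are not touched.

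**What to change.** Three changes, with both protocol 8.6 checks kept:

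1. In SAP 5.4, state that the rate applies to subjects who were alive and re-consented at re-contact after their 30-day exit. Word the objective and the report's conclusion to match.
2. In SAP 5.5 item 4, run the protocol 8.6 comparison (baseline, procedural and 30-day variables) also within the eligible set, meaning invited sites and the sponsor's window. Compare re-enrolled with eligible but not re-enrolled subjects, descriptively and with the imprecision stated.
3. Beside it, report the numbers eligible, re-enrolled, died before contact, declined, not reached and not contacted, as far as sites hold this and local ethics rules allow.

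Item 1 is wording. Item 2 uses data already held. Item 3 asks invited sites for counts by reason, which is some extra work because these subjects signed no addendum; the SAP says follow-ups are still being completed, so contact outcomes can still be recorded. The drawback is a small comparison group that may settle little on its own.
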